10.2 Other Efficacy Endpoints

Not applicable.

10.3 Adjustments for Covariates

In the analysis of the incidence of success in IGA, the Cochran-Mantel-Haenszel test stratified by baseline IGA (mild or moderate) will be conducted.

10.4 Subgroup Analysis

Incidence of success in IGA will also be analyzed in the following subgroups in the same manner as described in [Section 10.1.1](#).

Age: <7 or ≥7 years old

Gender: Male or female

Baseline IGA score: 2 (mild) or 3 (moderate)

11 Pharmacokinetic Analyses

11.1 Pharmacokinetics Analysis Set

The pharmacokinetic analysis set consists of all subjects who have received the IMP at least once and have at least one evaluable plasma drug concentration measured.

11.2 Pharmacokinetic Endpoints

- Plasma trough concentration of OPA-15406 (predose at Week 1 and Week 4)

11.3 Method of Calculation of Pharmacokinetic Endpoints

- 1) Plasma concentrations below the lower limit of quantification will be treated as zero (ng/mL) for the calculation of descriptive statistics.
- 2) Plasma trough concentrations will be handled as follows:
 - If the time of the blood sampling was within 6 hours from the last IMP administration, the sampling point will be excluded from the analysis.
 - If the treatment area (%) was changed (including non-compliance of IMP) within 3 days before the sampling point, the sampling point will be excluded from the analysis.
- 3) The timepoint of blood sampling for the pharmacokinetic endpoint at withdrawal will be handled as follows: If the blood sampling at withdrawal meets neither of the exclusion criteria in (2) and falls within the allowable window shown below, the sampling point will be included in the analyses. If the blood sampling at

withdrawal coincides with any pharmacokinetic timepoint, the blood sampling at withdrawal will not be included in the analyses.

Timepoint	Study Day	Allowable Window (Day)		
Baseline	1		-	1
Week 1	8	4	-	22
Week 4	29	23	-	50

- 4) The dose used for the dose adjustment of concentration will be calculated as follows:

$$\text{Dose (mg)} = [\text{the subject's BSA (m}^2\text{)}] \times [\text{treatment area (\%)}] \times [10 \text{ g/m}^2] \times [\text{formulation strength (0.3\% or 1\%)}] \times 1000$$

11.4 Method of Display

- 1) When plotting the plasma drug concentration-time profile, arithmetic means and standard deviations will be used.
- 2) Descriptive statistics of the plasma trough concentrations and dose(mg)-normalized plasma trough concentrations will be calculated by treatment group and pharmacokinetic timepoint.
- 3) Descriptive statistics of the total treatment area (%) will be calculated by treatment group and pharmacokinetic timepoint.
- 4) In 2) or 3) above, when the number of analyzed subjects is zero (0), only the number of subjects will be calculated; when only one (1) subject is analyzed, only the number of subjects, arithmetic mean, and geometric mean will be calculated; and when two (2) subjects are analyzed, only the number of subjects, arithmetic mean, geometric mean, and maximum and minimum values will be calculated.

11.5 Handling of Values

Among descriptive statistics, the number of subjects will be displayed in integers, and minimum and maximum will be displayed as it is in the same number of digits (n-digit) as that of an individual value of the target data. For arithmetic mean, geometric mean, median, and standard deviation values, a value of “n + 1” figures will be rounded off to obtain a value of “n” figures so that the number of digits will be the same number of digits (n-digit) as that of an individual value of the target data. For coefficient of variation, 2 decimal places will be rounded to obtain 1 decimal place.

12 Rationale for Target Number of Subjects

12.1 Target Number of Subjects

60 subjects

12.2 Rationale for the Number of Subjects

The sample size of 20 subjects for each group, a total of 60 subjects, has been established in consideration of the feasibility of the trial and the number of subjects needed to evaluate efficacy and safety. Assuming that the probabilities of success in IGA for each group are the same as those in the phase 2 trial outside Japan (271-12-205), the expected incidence of success in the 1% OPA-15406 group, the 0.3% OPA-15406 group, and the vehicle group is 20.93%, 14.63%, and 2.7%, respectively. In that case, the probability of the 1% group > the vehicle group, the 0.3% group > the vehicle group, and the 1% group minus the vehicle group > 10% in the point estimate of incidence of success is 96.2%, 88.3%, and 71.5%, respectively. Also, the probability of the 1% group > the 0.3% group \geq the vehicle group in point estimate of incidence of success is 60.6%.

13 Changes From Analysis Planned in the Protocol

13.1 Changes From the Efficacy Analyses Planned in the Protocol

- The factors/covariates included in the MMRM or ANCOVA model were described consistently. A categorical variable included in the model was described as a factor, and a continuous variable as a covariate.

Rationale for change: To further clarify the analytical methods

13.2 Changes From the Pharmacokinetic Analyses Planned in the Protocol

- The descriptive statistics of the plasma trough concentrations of OPA-15406 will not be calculated by affected BSA at baseline. The plasma trough concentrations of OPA-15406 will be normalized by dose (mg), not by affected BSA.

Rationale for change: Calculation of dose-normalized plasma trough concentration was considered adequate, the concentrations will not be computed by or normalized by affected BSA.

- The descriptive statistics for age, treatment area at baseline, and amount of administration will not be calculated by the affected BSA.

Protocol 271-102-00002

Rationale for change: These were considered not necessary for interpretation of the data.

- The descriptive statistics of total treatment area (%) will be calculated by treatment group and pharmacokinetic timepoint.

Rationale for change: These were considered necessary for interpretation of the data.

14 References

Not applicable.

15 Revision History

Not applicable.

Table 15-1 Revision History					
Version Number	Date of Revision	Section	Original Description	Revised Description	Reason for Revision
-	-	-	-	-	-

16 Appendix

16.1 Criteria for Potentially Clinically Significant

Table 16.1-1 Criteria for Potentially Clinically Significant Vital Sign Abnormalities		
TEST	CRITERIA 1	CRITERIA 2
DIASTOLIC BLOOD PRESSURE (MMHG)	DIASTOLIC BLOOD PRESSURE (mmHg) < 50 AND DECREASE \geq 15	DIASTOLIC BLOOD PRESSURE (mmHg) > 105 AND INCREASE \geq 15
HEART RATE (BEATS/MIN)	HEART RATE (BPM) < 50 AND DECREASE \geq 15	HEART RATE (BPM) > 120 AND INCREASE \geq 15
SYSTOLIC BLOOD PRESSURE (MMHG)	SYSTOLIC BLOOD PRESSURE (mmHg) < 90 AND DECREASE \geq 20	SYSTOLIC BLOOD PRESSURE (mmHg) > 180 AND INCREASE \geq 20
TEMPERATURE (°C)	-	TEMPERATURE (°C) \geq 37.8 AND INCREASE \geq 1.1°C
WEIGHT (KG)	WEIGHT (kg) DECREASE \geq 7%	WEIGHT (kg) INCREASE \geq 7%

Table 16.1-2 Criteria for Potentially Clinically Significant ECG Abnormalities		
CLASSIFICATION	CATEGORY	CRITERIA
VENT RATE OUTLIERS	NOTABLE INCREASES	25% INCREASE FROM BASELINE AND VENTRICULAR RATE > 100 BPM
VENT RATE OUTLIERS	NOTABLE DECREASES	25% DECREASE FROM BASELINE AND VENTRICULAR RATE < 50 BPM
PR OUTLIERS	NOTABLE CHANGES	\geq 25% CHANGE FROM BASELINE WHEN PR > 200 MSEC
QRS OUTLIERS	NOTABLE CHANGES	\geq 25% CHANGE FROM BASELINE WHEN QRS > 100 MSEC
QT	NEW ONSET (\geq 450 MSEC)	NEW ONSET (\geq 450 MSEC) IN QT MEANS A SUBJECT WHO ATTAINS A VALUE \geq 450 MSEC DURING TREATMENT PERIOD BUT NOT AT EACH BASELINE
QTcB	NEW ONSET (\geq 450 MSEC) IN MALE OR (\geq 470 MSEC) IN FEMALE	NEW ONSET (\geq 450 MSEC IN MALE OR \geq 470 MSEC IN FEMALE) IN QTcB MEANS A SUBJECT WHO ATTAINS A VALUE \geq 450 OR \geq 470 MSEC DURING TREATMENT PERIOD BUT NOT AT EACH BASELINE
QTcB	NEW ONSET (\geq 450 MSEC) AND \geq 10% INCREASE	NEW ONSET (\geq 450 MSEC) AND \geq 10% INCREASE IN QTcB MEANS A SUBJECT WHO ATTAINS A VALUE \geq 450 MSEC AND \geq 10% INCREASE DURING TREATMENT PERIOD BUT NOT AT EACH BASELINE
QTcB	INCREASE 30 - 60 MSEC	INCREASE IN CHANGE FROM BASELINE VALUE \geq 30 AND \leq 60 MSEC
QTcB	INCREASE > 60 MSEC	INCREASE IN CHANGE FROM BASELINE VALUE > 60 MSEC

Table 16.1-2 Criteria for Potentially Clinically Significant ECG Abnormalities		
CLASSIFICATION	CATEGORY	CRITERIA
QTcF	NEW ONSET (≥ 450 MSEC) IN MALE OR (≥ 470 MSEC) IN FEMALE	NEW ONSET (≥ 450 MSEC IN MALE OR ≥ 470 MSEC IN FEMALE) IN QTcB MEANS A SUBJECT WHO ATTAINS A VALUE ≥ 450 OR ≥ 470 MSEC DURING TREATMENT PERIOD BUT NOT AT EACH BASELINE
QTcF	NEW ONSET (≥ 450 MSEC) AND $\geq 10\%$ INCREASE	NEW ONSET (≥ 450 MSEC) AND $\geq 10\%$ INCREASE IN QTcB MEANS A SUBJECT WHO ATTAINS A VALUE ≥ 450 MSEC AND $\geq 10\%$ INCREASE DURING TREATMENT PERIOD BUT NOT AT EACH BASELINE
QTcF	INCREASE 30 - 60 MSEC	INCREASE IN CHANGE FROM BASELINE VALUE ≥ 30 AND ≤ 60 MSEC
QTcF	INCREASE > 60 MSEC	INCREASE IN CHANGE FROM BASELINE VALUE > 60 MSEC

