### 3.4.2 Inclusion Criteria

Subjects are required to meet the following inclusion criteria #1 through #5 in Table 3.4.2-1 at the screening examination, and #6 and #7 at the screening examination and the baseline examination.

Table 3.4.2-1 Inclusion Criteria	
1	Sex: Either male or female
2	Hospitalization status: Outpatient
3	Age: 2 to 14 years, inclusive (at time of obtaining informed consent)
4	Diagnosis of AD based on the criteria of Hanifin and Rajka  (Appendix 1)
5	Subjects whose legal guardian is able to provide informed consent prior to participation in the trial
6	AD affecting $\geq 5\%$ to $\leq 40\%$ of BSA
7	IGA score of 2 (mild) or 3 (moderate)

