9	Subjects who are judged by the investigator or subinvestigator to have a clinically abnormal blood pressure or pulse rate at the screening examination
10	Subjects who are judged by the investigator or subinvestigator to be problematic in withdrawing blood
11	Subjects who are unable to stop using topical corticosteroids, topical immunomodulators, topical retinoids and topical antihistamine from 7 days prior to the baseline examination until the Week 4 examination. Low or medium potency corticosteroids in the Guidelines for Management of Atopic Dermatitis  may be used until 4 days prior to the baseline examination in the judgment of the investigator or subinvestigator for the gradual decrease in the screening period before stopping.
12	Subjects who are unable to stop using systemic corticosteroids, systemic immunomodulators, systemic antimetabolites, systemic retinoids, and biologics from 28 days prior to the baseline examination until the Week 4 examination. Intra-ocular, intra-nasal and intra-auricular or inhaled corticosteroids may be considered if, in the opinion of the investigator or subinvestigator, their use will not impact assessment of the affected area.
13	Subjects who are unable to stop treatment with ultraviolet A , narrowband ultraviolet B, and ultraviolet B from 28 days prior to the baseline examination until the Week 4 examination
14	Subjects who are unable to continue in the trial without changing the dosage and administration of systemic antihistamines, sodium cromoglicate, tranilast, or suplatast tosilate from 7 days prior to the baseline examination until the Week 4 examination. Intra-ocular, intra-nasal, or inhalant formulations may be considered if, in the opinion of the investigator or subinvestigator, their use will not impact the assessment of the affected area.
15	Subjects with known hypersensitivity (including history) to any drugs (prescription, OTC, etc) or any ingredient of OPA-15406 ointment (eg, white petrolatum, mineral oil, paraffin, white wax, or propylene carbonate)
16	Subjects with known plans to receive any of the prohibited concomitant drugs or therapies during the trial period
17	Subjects who have used any other investigational drug within 4 months prior to the baseline examination or who are scheduled to participate in any other clinical trial during the trial period
18	Subjects who have never been treated with a prescription medication for AD or who are satisfied with their current AD treatment regimen

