9.6 Vital Signs (Including Body Weight)

Measured values and changes from baseline in body weight, body temperature, blood pressure (systolic/diastolic), and pulse rate at each timepoint will be summarized for the overall population and by treatment group using descriptive statistics. For body temperature, blood pressure (systolic/diastolic), and pulse rate, the number and percentage of subjects with potentially clinically significant vital sign abnormalities (Table 16.1-1) will be computed for the overall population and by treatment group. A listing of subjects with potentially clinically significant abnormalities will be provided.

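### The high blood-pressure flags in SAP Table 16.1-1 use one fixed limit for ages 2 to 14, so a zero in those rows says little about a moderate rise

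*SAP*

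**What the plan says.** Protocol 3.4.2 enrols "Age: 2 to 14 years, inclusive (at time of obtaining informed consent"), and Protocol 3.3.1 asks for at least 8 of the 60 subjects to be aged 2 to 6. Safety is the primary objective, and the primary endpoint is the number and percentage of subjects with adverse events.

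SAP 9.6 plans two things for vital signs: descriptive statistics of values and changes at each timepoint, and, for temperature, blood pressure and pulse, "the number and percentage of subjects with potentially clinically significant vital sign abnormalities", overall and by treatment group. The criteria are in Table 16.1-1 (SAP 16.1). Each row joins an absolute limit to a change from baseline, and both must be met:

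- high systolic: "SYSTOLIC BLOOD PRESSURE (mmHg) > 180 AND INCREASE" of at least 20;
- high diastolic: "DIASTOLIC BLOOD PRESSURE (mmHg) > 105 AND INCREASE" of at least 15;
- low systolic: "SYSTOLIC BLOOD PRESSURE (mmHg) < 90 AND DECREASE" of at least 20;
- low diastolic: "DIASTOLIC BLOOD PRESSURE (mmHg) < 50 AND DECREASE" of at least 15;
- high heart rate: "HEART RATE (BPM) > 120 AND INCREASE" of at least 15.

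No row has an age band, and no reason for the limits is given. SAP 7.1, 8.1, 9.3 and 10.4 split results at 7 years; SAP 9.6 states no such split.

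**The concern.** One absolute limit per direction is applied to a 2-year-old and a 14-year-old alike. The high blood-pressure limits are so far above the change sizes in the same rows that the change component has no effect upward. Downward, the absolute limit is much closer to the starting value. The display is therefore lopsided: a moderate fall can be counted, and a rise of the same size is not.

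Two things are at stake. A 0% in the high blood-pressure rows of a paediatric safety report can be read as evidence of no effect when the rule could hardly have produced any other answer. And the counts for low pressure and fast heart rate can differ between arms of about 20 because the arms differ in age. Protocol 3.6 names minimization but leaves its details to a separate specification, so the documents do not show that age is balanced.

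**Working it through.** The plan gives no expected count and no derivation for these limits, so there is no figure of its own to reproduce.

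**Step 1: the table's own numbers, no outside values.**

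- A value above 180 from a systolic baseline of 160 or less is a rise above 180 − 160 = 20. A value above 105 from a diastolic baseline of 90 or less is a rise above 105 − 90 = 15. From such baselines the change component is met automatically and the absolute limit decides. Protocol 3.4.3 excludes children judged "to have a clinically abnormal blood pressure or pulse rate at the screening examination".
- Illustration, systolic baseline 100: a fall of 20 gives 80, below 90, and is flagged; a rise must exceed 180 − 100 = 80.
- Illustration, diastolic baseline 60: a fall of 15 gives 45, below 50, and is flagged; a rise must exceed 105 − 60 = 45.

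**Step 2: expected flags.** The documents give no paediatric means or SDs. Assumed ranges: systolic mean 90 to 120, SD 8 to 15; diastolic mean 50 to 70, SD 8 to 12; heart rate mean 80 to 110, SD 10 to 14. Readings are taken as normal, with correlation 0.5 within a child and three on-treatment visits (Weeks 1, 2 and 4). The share of children meeting both components at any visit was simulated and multiplied by 60.

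As a hand check, the expected number of readings above a limit L is 60 × 3 × P(Z > (L − mean)/SD), which bounds the number of children:

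- Systolic, worst case (mean 120, SD 15): z = (180 − 120)/15 = 4.0, P = 3.17 × 10⁻⁵, bound 180 × P = 0.006. Simulated: 0.006.
- Diastolic, worst case (mean 70, SD 12): z = 35/12 = 2.92, P = 0.00177, bound 0.32. Simulated: 0.20.
- Systolic with every child raised by 20 (mean 120, SD 15): z = 40/15 = 2.67, P = 0.00383, bound 0.69. Simulated: 0.6. At SD 10 and the same mean it is 0.007.
- Diastolic with every child raised by 15, SD 10: 0.01 at mean 50, 3.2 at mean 70. At mean 70 and SD 12 it is about 6.

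Flags among 60 untreated children in the other rows:

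| Row | Whole assumed range | SD held at 10, mean varied |
|---|---|---|
| Systolic < 90, fall ≥ 20 | 0.0 to 10.8 | 3.2 (mean 90) to 0.1 (mean 120) |
| Diastolic < 50, fall ≥ 15 | 0.3 to 12.2 | 8.4 (mean 50) to 1.4 (mean 70) |
| Heart rate > 120, rise ≥ 15 | 0.0 to 11.0 | 0.0 (mean 80) to 5.0 (mean 110) |

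The last column isolates the mean, which is the part that would move with age.

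**Step 3: counting the change component alone.** At correlation 0.5 the SD of a change is SD × √(2 × 0.5) = SD.

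- No effect, systolic, SD 10: P(change ≥ 20) = P(Z ≥ 2) = 0.0228 per visit, bound 180 × 0.0228 = 4.1 children. Simulated: about 3 of 60 per direction. At SD 15: about 12.
- No effect, heart rate ±15: about 9 of 60 per direction at SD 10 and about 18 at SD 14. Diastolic uses the same 15, so it is also about 9 at SD 10.
- Every child raised by exactly 20: a child is missed only if the baseline error is the largest of four exchangeable values, with probability 1/4. So 60 × 3/4 = 45 are counted, whatever the SD.

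At SD 10 the change-only count therefore moves from about 3 to about 45 of 60 under a 20 mmHg rise, while the planned high systolic count stays at or near zero.

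**The case against.** A reader might infer that the planned count must read zero whatever the drug does, because no child can reach the limits. The documents do not support that. The SAP 9.6 count also covers low pressure, pulse and temperature, which children can meet. The diastolic limit can be reached at the top of the assumed range: 0.20 expected flags among 60 untreated children is roughly an 18% chance of at least one (1 − e^−0.20). A large systolic effect would show too: a 40 mmHg rise in every child flags about 12 of 60 at mean 120 and SD 15, though only 0.004 at mean 100 and SD 10. How reachable the limits are rests on assumed values.

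Nor would a single large rise be hidden. The SAP defines descriptive statistics to include the minimum and maximum, so a 40 mmHg rise in one child would appear in the maximum change, although it moves the mean of an arm of 20 by only 40/20 = 2 mmHg. PDATA-7 lists vital signs, and a mean effect would show in the planned change summaries.

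It would also be wrong to say that small children are flagged low merely for being small. A stable systolic of 88 is never flagged, because a fall of at least 20 is also required.

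Finally, this is a secondary display: the primary endpoint does not use Table 16.1-1, and Protocol 7.6.3 plans descriptive statistics only. All of this stands, and it limits the point. It leaves one gap: neither the maximum nor the listing says how many children rose, and the table meant to count them scarcely can in the upward direction.

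**Conclusion.** The point holds for the high blood-pressure rows, most firmly for systolic. Step 1 needs nothing beyond the table: from any systolic baseline of 160 or less, or diastolic of 90 or less, the absolute limit alone decides. Under the assumed ranges a zero above 180 is expected with no effect and, in nearly all scenarios, with a 20 mmHg rise in every child. The same is largely true above 105, except near the top of the diastolic range. Such a zero should not be reported as reassurance about a moderate rise.

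The low-pressure and high-heart-rate rows have the opposite weakness. Their chance counts run from 0 to about 12 of 60 and vary with the assumed mean, so they can reflect the ages in an arm.

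The counts rest on assumed means and SDs, normality and a correlation of 0.5; the baseline arithmetic and the 45 of 60 do not rest on the assumed means and SDs. This is a should-fix item for a secondary safety display. It does not affect the primary endpoint.

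**What to change.** In SAP 9.6:

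1. Add a table, by arm and age group (<7, ≥7), of children meeting the change components of Table 16.1-1 alone: systolic ±20, diastolic ±15, heart rate ±15, each direction separately.
2. Replace the fixed absolute limits used for this analysis flag by age-appropriate ones from a cited reference, or state why fixed limits suit ages 2 to 14. The choice is the sponsor's; none is proposed here. These are analysis flags and do not alter how any child is managed.

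The cost is SAP text and programming on data already collected, and SAP 4 allows changes until database lock. The downside is more chance flags: about 3 of 60 per direction for systolic at SD 10 (about 1 per arm of 20), up to about 12 at SD 15, and about 9 to 18 of 60 for heart rate (3 to 6 per arm). The counts should therefore be read against the vehicle arm. With as few as 8 children aged 2 to 6 across three arms, the younger cells may hold only two or three children each and can only be descriptive.
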